7.1.2 Form

Recombinant human IL-2 (Aldesleukin) (Proleukin®: Novartis Inc., & Prometheus Laboratories, Inc) is supplied as a sterile, white to off-white, lyophilized cake in single-use vials containing 22 MIU of aldesleukin.

CONFIDENTIAL

This document is confidential. Do not disclose or use except as authorized.

For the 22 million international unit (MIU) vial, when reconstituted with 1.2 mL Sterile Water for Injection (SWFI), each mL contains 18 MIU (1.1mg) IL-2, 50 mg mannitol and ~180 mcg sodium dodecyl sulphate, buffered with ~170 mcg sodium phosphate monobasic and 890 mcg sodium phosphate dibasic to a pH of 7.5 (range: 7.2-7.8)

7.1.3 Storage and Stability

Store vials of lyophilized IL-2 in a refrigerator at 2-8°C (36-46°F). Do not use beyond the expiration date printed on the label. Vials should be entered only once for reconstitution to minimize the chances of contamination. If not used immediately, in-use storage times should normally not be longer than 24 hours at 2-8°C, unless reconstitution has been performed under controlled and validated aseptic conditions in a laminar airflow hood.

Data support stability and sterility of reconstituted diluted IL-2 preparations (reconstituted with SWFI and further diluted with D5W); and the stability and sterility of product reconstituted with SWFI but not further diluted, for up to 14 days at 2-8°C (36-46°F) when single-use syringes for daily use are prepared by qualified health-care professionals under aseptic conditions (per Proleukin® Investigator's Brochure (Chiron Corporation, 10 Sep 2003, pp113).

Therefore, reconstitution and dilution of lyophilized IL-2 is to be performed under controlled and validated aseptic conditions in a laminar flow hood per DFCI pharmacy policy and procedure manual . The dose or doses thus prepared and stored at 2-8°C (36-46°F) need to be used within 14 days.

7.1.4 Compatibility

IL-2 should be reconstituted with sterile water for injection (SWFI) plus D5W. Reconstitution or dilution with Bacteriostatic Water for Injection or 0.9% Sodium Chloride for Injection should be avoided due to increased aggregates.

IL-2 is not given IV, or in combination with other agents, hence compatibility issues are not applicable.

7.1.5 Handling

The single-daily-use syringes containing reconstituted and diluted solutions should be stored in a refrigerator at 2-8°C. DO NOT FREEZE. The product

CONFIDENTIAL

This document is confidential. Do not disclose or use except as authorized.

Phase II ECP and IL-2 for chronic GVHD

Version 2.0; August 15, 2016

should be inspected visually for particulate matter or discoloration and brought to room temperature before administration.

7.1.6 Availability

IL-2 (Proleukin®) is a commercial agent

7.1.7 Preparation

[figure not shown]
IL-2 will be reconstituted in 1 ml Becton Dickinson single use syringes. All IL-2

7.1.8 Administration

After reconstitution, an up to 2-week IL-2 supply will be provided in single-use syringes (in a cool-pack if necessary), for home refrigerator storage at 2-8 C. One single-use syringe will be used each day during home SC self-administration, and discarded in the sharps' containers provided. Participants will be instructed to rotate injection sites, if feasible.

7.1.9 Ordering

CONFIDENTIAL

This document is confidential. Do not disclose or use except as authorized.

7.1.10 Accountability

The investigator, or a responsible party designated by the investigator, must maintain a careful record of the inventory and disposition of the agent (investigational or free of charge) using the NCI Drug Accountability Record or another comparable drug accountability form.

7.1.11 Destruction and Return

At the end of the study, unused supplies of IL-2 should be destroyed according to institutional policies. Destruction will be documented in the Drug Accountability Record Form.

CONFIDENTIAL

This document is confidential. Do not disclose or use except as authorized.

8. CORRELATIVE/SPECIAL STUDIES

Investigational blood samples will be processed and banked with the Pasquarello Tissue Laboratory at DFCI. Please refer to the study operations manual for details regarding processing and handling of study specimens.

8.1 Pharmacokinetic Studies

N/A

8.2 Pharmacodynamic Studies

N/A

CONFIDENTIAL

This document is confidential. Do not disclose or use except as authorized.

Phase II ECP and IL-2 for chronic GVHD
Version 2.0; August 15, 2016

9. STUDY CALENDAR

Table 2: Summary of Required Data

	Within 4 Wks prior (baseline)	During Therapy (End of Wks 1, 2, 4, 6, 8, 9, 10, 12, 14) ^a	End of Wk 16 ^a	Extended-duration IL-2 (4 Wkly) ^c
Medical History	X	X	X	X
Physical Exam	X	X	X	X
Toxicity Assessment		X	X	X
cGVHD Symptom Score	X	X ^b	X	X [#]
EKG	X			
Pregnancy Test [¶]	X			
Pulmonary Function	o	o ^b	o	o [#]
Dermatologic Assessment	o	o ^b	o	o [#]
Oral Assessment	o	o ^b	o	o [#]
Flexion Assessment	o	o ^b	o	o [#]
Ocular Assessment	o	o ^b	o	o [#]
CBC with Diff	X	X*	X	X
Serum Chemistry	X	X*	X	X
Quantitative Immune Globulins	X	X ^d	X	X ^δ
Immunology ¹	X	X	X	X ^δ
Steroid Assessment ²	X	X ^b	X	X ^δ
CMV Viral Load	X	X	X	X
Thyroid Function	X		X	X ^δ
Drug Diary ⁺		X	X	X

X- Required Evaluation

o- Required for patients with clinical involvement of these organ systems (oral and ocular assessments are optional), Baseline pulmonary function tests can be scheduled up to 4 weeks prior to start of treatment to 1 week after for scheduling flexibility.

1 Immunology: plasma banking; storage of additional mononuclear cells.

2 Systemic steroids should not be tapered unless there is toxicity, e.g severe hyperglycemia (with permission of study PI).

a Testing at end of weeks 1, 2, 4, 6, 8, 9, 10, 12, 14 will be performed ± 4 days, to allow for scheduling and administrative flexibility around weekends, holidays etc.

b Week 8 for steroid dose and cGVHD assessments.

c Testing during extended-duration therapy will be performed ± 2 weeks, to allow for scheduling and administrative flexibility around patient travel, work, holidays etc.

d Week 4, 8, 12.

CONFIDENTIAL

This document is confidential. Do not disclose or use except as authorized.

Phase II ECP and IL-2 for chronic GVHD

Version 2.0; August 15, 2016

* Laboratory testing of CBC/manual diff, serum creatinine and LDH will also be performed 4±2 days after IL-2 initiation, to assess for anemia, thrombocytopenia, schistocytes and/or renal dysfunction associated with thrombotic microangiopathy.

δ Every 8 weeks (±4 weeks) at time of mandatory study-center follow-up.

Every 16 weeks (+/- 4 weeks) during year 1 at time of mandatory study-center follow-up.

¶ For women of child-bearing potential.

+ To be completed and returned to clinic at least every 2 weeks during study IL-2 treatment. To be completed at and returned to clinic at least every 8 weeks for extended-duration IL-2.

CONFIDENTIAL

10. MEASUREMENT OF EFFECT

Evaluable for toxicity- Participants who receive at least one dose of IL-2 will be evaluable for toxicity of IL-2 treatment.

Evaluable for response- Participants who have received at least 4 weeks of ECP+IL-2 and have had their disease re-assessed will be considered evaluable for combination ECP+IL-2 response. These participants will have their response classified according to the definitions stated below

10.1 cGVHD Assessments

Patients will undergo standardized cGVHD assessment per NIH guidelines (e.g., http://asbmt.affiniscape.com/associations/11741/files/ResponseCriteriaAPPENDIXAFor_mA.pdf) at baseline and week 8 and 16 on study.⁴⁶ cGVHD response will be assessed per NIH consensus criteria.⁴⁷ Of note, oral and ocular sites will not be included in determination of response, as additional topical therapy is permitted for those sites.

10.1.1 Complete response is defined as- Organ response: resolution of all reversible manifestations related to cGVHD in a specific organ; Overall response: resolution of all reversible manifestations in each organ or site of cGVHD involvement. Depending on relevant organ system involvement, patients will undergo repeat detailed assessment of ocular, oral, cutaneous, musculoskeletal and pulmonary systems.

10.1.2 Partial response is defined as- Organ response: at least 50% improvement in the scale used to measure disease manifestations related to cGVHD (e.g. a 50% decrease in skin rash from 80% BSA to 40% BSA), with a minimum of 25% improvement in the full scale as opposed solely to a percentage of the starting value (Appendix F; Section 17.6); Overall response: improvement in measure at least one organ or site, without progression in measures at any other organ or site. Of note, for global ratings and categorical scales, a 1-point change in a 3- or 7- point scale or a 2- to 3- change on a 0- to 10- point scale (0.5 SD change) would be considered clinically meaningful. Additionally, the hallmark for response to therapy for bronchiolitis obliterans syndrome (BOS) is stabilization of lung function with no further decrease in FEV1 during a 3-month period.

10.1.3 Non-responders (e.g., minor response, stable disease) will not have changes in cGVHD meeting NIH criteria for partial response or disease progression.

10.1.4 Progressive disease- Organ progression: an absolute increase of at least 25% in the scale used to measure disease manifestations related to cGVHD (Appendix G; Section 17.7). Of note, for global ratings and categorical scales, a 1-point change in a 3- or 7- point scale or a 2- to 3- change on a 0- to 10- point scale (0.5 SD change) would be considered

CONFIDENTIAL

This document is confidential. Do not disclose or use except as authorized.

Phase II ECP and IL-2 for chronic GVHD

Version 2.0; August 15, 2016

clinically meaningful. Additionally, ‘clinical worsening of cGVHD’ is not synonymous with progressive cGVHD per NIH criteria, as patients may experience worsening symptoms that do not meet objective NIH criteria for progression. If so, they still have the option of discontinuation of IL-2 and initiating additional immunosuppression for lack of IL-2 efficacy; at the judgment of the treatment physician, as per section 6.2.

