3. PARTICIPANT SELECTION

3.1 Eligibility Criteria

Participants must meet the following criteria on screening examination to be eligible to participate in the study:

- 3.1.1 Recipients of 7-8/8 HLA matched adult donor allogeneic stem cell transplantation with myeloablative or non-myeloablative conditioning regimens.
- 3.1.2 Participants must have steroid-refractory cGVHD. Steroid-refractory cGVHD is defined as having persistent signs and symptoms of cGVHD (Appendix D; section 17.4) despite the use of prednisone at ≥ 0.25 mg/kg/day (or 0.5 mg/kg every other day) for at least 4 weeks (or equivalent dosing of alternate corticosteroids) without complete resolution of signs and symptoms. Patients with either extensive chronic GVHD or limited chronic GVHD requiring systemic therapy are eligible.
- 3.1.3 Stable dose of corticosteroids for 4 weeks prior to enrollment. Exception permitted with overall PI approval.
- 3.1.4 No addition or subtraction of other immunosuppressive medications (e.g., calcineurin-inhibitors, sirolimus, mycophenolate-mofetil) for 4 weeks prior to enrollment. The dose of immunosuppressive medicines may be adjusted based on the therapeutic range of that drug
- 3.1.5 Patient age ≥ 18 years old. Because no dosing or adverse event data are currently available on the use of IL-2 in participants <18 years of age, children are excluded from this study.
- 3.1.6 Estimated life expectancy greater than 3 months.
- 3.1.7 ECOG performance status 0-2 (Appendix A; section 17.1).
- 3.1.8 Participants must have adequate organ function as defined below:
 - Hepatic: Adequate hepatic function (total bilirubin <2.0 mg/dl-exception permitted in patients with Gilbert's Syndrome; AST (SGOT)/ALT (SGPT) $\leq 2x$ ULN), unless hepatic dysfunction is a manifestation of presumed cGVHD. For patients with abnormal LFTs as the sole manifestation of cGVHD, documented GVHD on liver biopsy will be required prior to enrollment. Abnormal LFTs in the context of active cGVHD involving other organ systems may also be permitted if

CONFIDENTIAL

This document is confidential. Do not disclose or use except as authorized.

Phase II ECP and IL-2 for chronic GVHD

Version 2.0; August 15, 2016

the treating physician documents the abnormal LFTs as being consistent with hepatic cGVHD, and a liver biopsy will not be mandated in this situation.

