14. STATISTICAL CONSIDERATIONS

14.1 Study Design/Endpoints

This is a one-stage Phase II trial to assess the efficacy of 16 weeks extracorporeal photopheresis (ECP) with the addition of daily low-dose subcutaneous (SC) interleukin-2 (IL-2) for weeks 8-16 in patients with steroid-refractory chronic graft-versus-host disease (cGVHD). The primary endpoint is overall response as defined in Section 10.0. Response will be evaluated at 16 weeks of treatment.

Our previous studies of low-dose IL-2 alone (DFCI#07-083, 11-149) for steroid refractory cGVHD showed a overall response rate of ~50-60%, and a randomized phase 2 trial of ECP vs. placebo showed a 40% response rate of skin cGVHD and 33% response rate of non-skin cGVHD⁴³. Conservatively extrapolating this information, we would consider ECP+IL-2 potentially efficacious if the overall response rate is 75% or higher and unworthy if 50% or lower. With 25 evaluable patients, if 17 or more patients respond, the treatment will be considered efficacious for the treatment of steroid refractory cGVHD.

With this design, the probability of concluding the treatment efficacious is 0.85 if the true but unknown response rate is 75% and 0.05 if the true rate is 50%. This decision rule is calculated using the exact binomial method. Table 1 below presents the operating characteristics of this design. Patients will be considered evaluable for response if they receive at least one week of ECP, which we anticipate to occur to all patients based on our prior experience. Patient will be replaced if the patient is removed from the study for reasons unrelated to the treatment (see Section 5.4).

Table 1. Operating Characteristics

	True but Unknown Response Rate						
	50%	55%	60%	65%	70%	75%	
Prob(≥ 17 responses in 25)	0.05	0.13	0.27	0.47	0.68	0.85	

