17.4 Appendix D: DEFINITE AND PROBABLE cGVHD MANIFESTATIONS

Organ System	Definite manifestations of chronic GVHD	Possible manifestations of chronic GVHD
Skin	Scleroderma (superficial or fasciitis), lichen planus, vitiligo, scarring alopecia, hyperkeratosis pilaris, contractures from skin immobility, nail bed dysplasia	Eczematoid rash, dry skin, maculopapular rash, hair loss, hyperpigmentation
Mucous membranes	Lichen planus, non-infectious ulcers, corneal erosions/non-infectious conjunctivitis	Xerostomia, keratoconjunctivitis sicca
GI tract	Esophageal strictures, steatorrhea	Anorexia, malabsorption, weight loss, diarrhea, abdominal pain
Liver	None	Elevation of alkaline phosphatase, transaminitis, cholangitis, hyperbilirubinemia
GU tract	Vaginal stricture, lichen planus	Non-infectious vaginitis, vaginal atrophy
Musculoskeletal /Serosa	Non-septic arthritis, myositis, myasthenia, polyserositis, contractures from joint immobilization	Arthralgia
Hematologic	None	Thrombocytopenia, eosinophilia, autoimmune cytopenias
Lung	Bronchiolitis obliterans	Bronchiolitis obliterans with organizing pneumonia, interstitial pneumonitis

CONFIDENTIAL

This document is confidential. Do not disclose or use except as authorized.

Phase II ECP and IL-2 for chronic GVHD
Version 2.0; August 15, 2016

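### Eligibility admits patients whose only cGVHD is oral or ocular, but the response definition excludes those sites and the plan still counts such patients among the 25

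*Combined protocol and SAP*

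**What the plan says.** **Who can enter.** Section 3.1.2 defines steroid-refractory disease by persistent signs and symptoms from Appendix D, with no restriction by organ. It adds: "Patients with either extensive chronic GVHD or limited chronic GVHD requiring systemic therapy are eligible". The mucous-membrane row of Appendix D (17.4) gives as definite manifestations "Lichen planus, non-infectious ulcers, corneal erosions/non-infectious conjunctivitis". No criterion in 3.1 or 3.2 asks for involvement outside the mouth and eyes.

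**What counts as response.** Section 10.1 states that "oral and ocular sites will not be included in determination of response, as additional topical therapy is permitted for those sites". Overall partial response (10.1.2) is "improvement in measure at least one organ or site, without progression in measures at any other organ or site". Section 10.1.3 describes non-responders as patients who "will not have changes in cGVHD meeting NIH criteria for partial response or disease progression". Overall complete response (10.1.1) requires all reversible manifestations to have resolved at every involved organ or site.

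**Who is in the denominator.** Section 10 counts as evaluable "Participants who have received at least 4 weeks of ECP+IL-2 and have had their disease re-assessed". Section 14.1 says: "Patients will be considered evaluable for response if they receive at least one week of ECP". The two rules differ from each other, but neither mentions a scorable site. Replacement under 14.1 is limited to removal from study for reasons unrelated to treatment. Lack of a scorable site is not among the removal criteria in 5.4.

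**The decision rule.** Section 14.1 says: "we would consider ECP+IL-2 potentially efficacious if the overall response rate is 75% or higher and unworthy if 50% or lower". Success is 17 or more responders among 25 evaluable patients.

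**The concern.** The entry criteria and the primary endpoint do not describe the same patients. Someone with disease only in the mouth or eyes can be registered, treated and counted as evaluable, yet has no site at which 10.1 allows an improvement to be scored. The documents do not say how to classify this patient.

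With one fixed cut-off in 25 patients, each place matters. A place that cannot yield a response means that 17 responders must come from fewer patients, so a treatment that works in scorable disease could miss the cut-off. If the gap were instead settled in the patient's favour at analysis, the rule would become easier to pass than planned. Either way, the operating characteristics in Table 1 would no longer describe the test actually applied to patients with scorable disease.

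**Working it through.** **Inputs.** From 14.1: n = 25, success at 17 or more responders, rates 50% and 75%, exact binomial method. Assumed: k, the number of patients among the 25 whose only disease is oral or ocular. The documents give no value; k = 0 is possible, and k = 1 and 2 are shown as illustrations.

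**Step 1: reproduce the plan's figures.** P(Bin(25, p) ≥ 17) at p = 50, 55, 60, 65, 70 and 75% is 0.0539, 0.1340, 0.2735, 0.4668, 0.6769 and 0.8506. All six agree with Table 1 at two decimals. The stated design is correct for an overall response rate in all 25 patients.

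**Step 2: natural reading.** Partial response needs improvement in at least one organ or site. With mouth and eye removed, no site is left to improve, so partial response is out of reach and the patient falls among the non-responders of 10.1.3. If p is the response rate among the 25 − k scorable patients:

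- Overall rate = p × (25 − k)/25
- Chance of success = P(Bin(25 − k, p) ≥ 17)
- Observed rate needed among scorable patients = 17/(25 − k)

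| k (assumed) | Overall rate if p = 75% | Power, p = 75% | Type I error, p = 50% | Needed among scorable |
|---|---|---|---|---|
| 0 | 0.75 × 25/25 = 75% | 0.851 | 0.054 | 17/25 = 68.0% |
| 1 | 0.75 × 24/25 = 72% | 0.766 | 0.032 | 17/24 = 70.8% |
| 2 | 0.75 × 23/25 = 69% | 0.654 | 0.017 | 17/23 = 73.9% |

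Solving P(Bin(25 − k, p) ≥ 17) = 0.8506 for p, the rate among scorable patients would have to be 77.6% (k = 1) or 80.3% (k = 2), in place of 75%, to keep the planned power.

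**Step 3: alternative reading.** If complete response in 10.1.1 is taken as met by default when no involved site counts, the k patients are automatic responders. The chance of success is then P(Bin(25 − k, p) ≥ 17 − k):

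| k (assumed) | Type I error, p = 50% | Power, p = 75% |
|---|---|---|
| 0 | 0.054 | 0.851 |
| 1 | P(Bin(24, 0.5) ≥ 16) = 0.076 | 0.879 |
| 2 | P(Bin(23, 0.5) ≥ 15) = 0.105 | 0.904 |

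The direction of the error therefore depends on a classification that the text does not make.

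**The case against.** **There may be no such patients.** Entry requires disease persisting through at least four weeks of systemic prednisone, and limited disease qualifies only if it needs systemic therapy. Treatment is twice-weekly photopheresis for 16 weeks. The rationale in 2.3 centres on skin, and the four patients described there as already on the combination had cutaneous disease. This stands: nothing suggests that oral- or ocular-only patients are expected in numbers. It does not exclude them. Single-organ disease is foreseen elsewhere: 3.1.8 sets a biopsy condition for patients whose sole manifestation is abnormal liver tests, but no condition is set for mouth or eye alone.

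**The 50% and 75% may already include them.** Section 14.1 states both as overall rates, drawn partly from two earlier trials of IL-2 alone. The eligibility that 2.2.1.4 describes for the first of these resembles 3.1.2. If those trials enrolled and scored such patients in the same way, Table 1 stands as it is. The documents do not give the earlier scoring rules, so this can be neither confirmed nor ruled out. The power loss is therefore conditional.

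**The checklist may close the gap.** Registration under 4.2 depends on an eligibility checklist that is not in the documents. The point is limited to the protocol text.

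**A stronger reading is tempting.** A reader might infer that these patients can never be responders whatever the treatment does, that they therefore do dilute the primary result, and that the error can only be conservative. The documents do not support that. Non-response follows from 10.1.2 and 10.1.3 but is not stated. Section 10.1.3 does not mention complete response, and 10.1.1 keeps ocular and oral examination in the repeat assessment. The default-complete-response reading is strained, but it is available and reverses the direction of the error.

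Excluding mouth and eye from response is reasonable, given that topical therapy is allowed there. The point is only that eligibility should match.

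**Conclusion.** The mismatch is real on the text and goes beyond a missing detail: following the plan as written can admit, and count, patients with no site at which improvement can be scored. Its practical size is unknown and may be nil.

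The loss of about 8 percentage points of power with one such patient, or about 20 with two, rests on three assumptions: that such patients are enrolled, that they are scored as non-responders, and that the 75% target refers to patients with a scorable site. On that reading the risk is a missed effect, and type I error falls. Only if they were scored as complete responders would type I error rise above the planned 0.054. This is a cheap improvement; it does not show that the design is unsound or that Table 1 is miscalculated.

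**What to change.** - **Section 3.1:** require at baseline at least one involved cGVHD organ or site, other than mouth or eye, that is assessable for response under 10.1. Record the qualifying site on the eligibility checklist.
- **Section 14.1:** for any patient already enrolled without such a site, state before responses are tabulated that the patient counts as a non-responder in the primary 17-of-25 analysis. This choice does not recover the lost power for those patients, but it rules out the type I error inflation and avoids exclusions after the fact.
- **Section 14.1:** add a descriptive sensitivity analysis, the response proportion with an exact confidence interval, excluding such patients.

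The cost is one eligibility line, one checklist field and a short addition to 14.1. The baseline cGVHD assessment is already required of every patient by 5.1.1, so no new procedure is needed. The downside is slightly narrower eligibility and possibly marginally slower accrual. If all 25 patients enter under the new criterion, all of them can respond and Table 1 applies as printed.

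A lighter alternative is to leave eligibility alone and only state the classification. That removes the ambiguity but leaves the possible loss of power.

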5.6 Criteria for Removal from Study

Participants will be removed from study when any of the criteria listed in Section 5.4 applies. The reason for study removal and the date the participant was removed must be documented in the study-specific case report form (CRF). Alternative care options will be discussed with the participant.

In the event of unusual or life-threatening complications, participating investigators must immediately notify the Principal Investigator.

[name] DPhil,

[REDACTED]
[REDACTED]

CONFIDENTIAL

This document is confidential. Do not disclose or use except as authorized.

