- Worsening of cGVHD: Clinical signs of worsening cGVHD while on IL-2 that require the addition of a new immunosuppressive medication (at the discretion of the treating physician), will be a criterion for IL-2 discontinuation. An increase in the corticosteroid dose above baseline will be considered evidence of worsening cGVHD. Changes in other immunosuppressive medication doses to maintain a therapeutic level alone will not be criteria for discontinuation of IL-2 or considered evidence of cGVHD worsening.
- Infection: Of note, infection during IL-2 treatment is not considered IL-2 related, since both cGVHD and the concurrent use of immune suppression medications are known risk factors for infection. Infection is therefore considered an expected complication of cGVHD. However, patients who develop a CTC grade 3 or higher infection prior to week 6 of IL-2 therapy will have IL-2 withheld. They can be considered for restarting IL-2 at their prior dose after control of infection, at the discretion of the treating physician.

CONFIDENTIAL

This document is confidential. Do not disclose or use except as authorized.

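### No rule scores systemic rescue before week 16, so a response reached after a corticosteroid increase can count toward the 17 of 25

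*Combined protocol and SAP*

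**What the plan says.** Section 14.1 takes the primary endpoint from Section 10 and fixes its timing: "Response will be evaluated at 16 weeks of treatment". The decision rule is: "With 25 evaluable patients, if 17 or more patients respond, the treatment will be considered efficacious".

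Section 10.1 defines complete response, partial response, non-response and progression by change in organ measures. The non-responder definition reads: "Non-responders (e.g., minor response, stable disease) will not have changes in cGVHD meeting NIH criteria for partial response or disease progression". None of the four categories mentions a new systemic agent or a higher steroid dose. Section 10.1.4 separates clinical worsening from NIH progression and then adds: "If so, they still have the option of discontinuation of IL-2 and initiating additional immunosuppression for lack of IL-2 efficacy".

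Three other sections bear on these patients:

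- Section 5.4 lists worsening that needs a new immunosuppressive medication among the reasons for ending ECP plus IL-2. It treats a corticosteroid increase as a sign of worsening.
- Section 5.6 then says: "Participants will be removed from study when any of the criteria listed in Section 5.4 applies".
- Section 6.2 says that worsening which needs a new immunosuppressant "will be a criterion for IL-2 discontinuation". It treats a steroid dose above baseline as a sign of worsening.

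There are two definitions of evaluable for response. Section 10 asks for at least 4 weeks of ECP plus IL-2 and a re-assessment. Section 14.1 asks for one week of ECP, and replaces only patients removed for reasons unrelated to treatment. Steroid dose is recorded at baseline, week 8 and week 16 (Section 10.3).

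**The concern.** The endpoint is meant to measure response to ECP plus IL-2. A patient whose cGVHD worsens, who gets more systemic treatment for it and is better at week 16, has not shown that response. The plan nevertheless has no wording that stops the week-16 organ scores from being read as a partial response.

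The protocol recognises the principle elsewhere. Section 10.1 leaves oral and ocular sites out of the response because extra topical therapy is allowed there. Section 5 says how to read stable or progressing cGVHD during a taper of other immunosuppression. Nothing says how to read an escalation.

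The trial has one arm, 25 patients and a fixed bar of 17, so a few patients scored one way or the other can decide the result. Without a written rule, they would be scored by judgement after their outcomes are known.

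**Working it through.** **Step 1. The plan's own figures.** Inputs from Section 14.1: "we would consider ECP+IL-2 potentially efficacious if the overall response rate is 75% or higher and unworthy if 50% or lower"; n = 25; bar = 17; exact binomial. The plan gives a chance of success of 0.85 at 75% and 0.05 at 50%.

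P(X ≥ 17) = Σ C(25,k) pᵏ(1−p)²⁵⁻ᵏ for k = 17 to 25:

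| True rate | 50% | 55% | 60% | 65% | 70% | 75% |
|---|---|---|---|---|---|---|
| Recomputed | 0.0539 | 0.1340 | 0.2735 | 0.4668 | 0.6769 | 0.8506 |
| Table 1 | 0.05 | 0.13 | 0.27 | 0.47 | 0.68 | 0.85 |

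All six agree to two decimals. No printed figure is wrong. The error at 50% is already slightly above 0.05.

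**Step 2. Following the patients through the text.**

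*Steroid increase, no new agent.* The trigger in 5.4 and 6.2 is a new immunosuppressive medication. The steroid sentence calls an increase a sign of worsening, but does not clearly make it a reason to remove the patient or stop IL-2. If the patient continues from the end of week 8 to week 16, that is 8 weeks of ECP plus IL-2, so the patient is evaluable under both definitions. If the organ scores meet partial response against baseline, the patient is a responder. An increase reversed between week 8 and week 16 would not appear in the scheduled steroid records.

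*New immunosuppressant.* 5.4 and 5.6 remove the patient. Neither section, nor 6.2, 10.1 or 14.1, says how the patient is scored. Under 14.1 the patient stays in the 25. Under Section 10 the patient can drop out of the evaluable set, through less than 4 weeks of ECP plus IL-2 or no re-assessment.

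**Step 3. Size if rescue-driven responses count.** The rates here are assumed, because the documents give none. Let f be the share of true non-responders who are rescued, and g the share of those who meet response at week 16. The apparent rate is p = 0.50 + 0.50 × f × g.

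| f | g | Apparent rate | P(≥17 of 25) |
|---|---|---|---|
| 10% | 25% | 51.25% | 0.069 |
| 20% | 25% | 52.5% | 0.087 |
| 20% | 50% | 55% | 0.134 |
| 30% | 50% | 57.5% | 0.196 |
| 40% | 50% | 60% | 0.274 |

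**Step 4. Size if failures leave the denominator under Section 10.** Assume that 12% of patients, all failures, are dropped and that accrual continues to 25 evaluable patients (the target in 14.2.1). The rate among those left is 0.50 / 0.88 = 56.8%, and P(≥17 of 25) = 0.178, about 0.18. Under 14.1 the same patients stay in the 25 and add nothing to the 17, so there is no inflation.

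**Step 5. With the scoring rule.** If rescue before week 16 is non-response and failures stay in the 25, the rule keeps 0.0539 at 50% and 0.8506 at 75%.

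**The case against.** A reader might infer that any rescued patient can become a responder, because 6.2 stops only IL-2 and the patient would then stay on ECP to week 16. The documents do not support that for a new agent. Section 6.2 does not say that ECP continues, and 5.4 with 5.6 removes the patient. The sections can be followed together. Improvement after a new agent enters the count only if an assessment after removal is made and used, which the text neither requires nor forbids. Likewise, a patient who flares at week 10 and stops IL-2 has had about 2 weeks of the combination and, unless IL-2 was started early, is not evaluable under Section 10.

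A reader might also infer that every lost outcome raises the rate. That holds only under the Section 10 definition of evaluable (Step 4).

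Three further objections carry weight:

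- Partial response is measured against baseline, not against the flare, and allows no progression elsewhere. A steroid-refractory patient must improve a good deal in a few weeks, so g may be small. A patient still in NIH progression at week 16 is not a responder in any case.
- The sizes rest on assumed rates. The low case, 0.069, is not far from 0.054.
- Section 10.1 applies NIH consensus criteria by reference. The absence of a rule is shown for the protocol text, not for that source.

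What stands is the steroid route, together with the missing score for removed patients. One could read the steroid sentence in 5.4 as a removal trigger in itself, but that patient would then also have no stated score.

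**Conclusion.** The concern holds in a limited form. The primary endpoint is not fully defined for patients who receive systemic rescue before week 16. Followed as written, the plan can count a response due to a steroid increase toward the 17. For patients removed after a new immunosuppressant, the gap is an unstated score and two conflicting evaluability definitions, not a clear route to being called a responder.

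At a true rate of 50%, the chance of declaring efficacy is 0.069 to 0.27 if rescue adds 1.25 to 10 percentage points. It is about 0.18 if 12% of patients, all failures, leave the denominator and are made up to 25. The reference is 0.054. These are illustrations under assumed rates, not estimates of what will happen. The direction is firm for the steroid route; the size is not known.

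**What to change.** Add to Sections 10.1 and 14.1:

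1. A participant who, before the week-16 assessment, receives a new systemic immunosuppressant or an above-baseline corticosteroid dose for cGVHD is a non-responder in the primary analysis.
2. A participant removed for worsening cGVHD, treatment-related toxicity, relapse or death without a week-16 assessment stays in the 25 as a non-responder.
3. State how item 1 applies when steroids are raised again after a taper, since Section 5 does not count progression during a taper of other immunosuppression as lack of efficacy.

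Record each steroid change with its date, in addition to the doses at baseline, week 8 and week 16. In the same edit, reconcile the evaluability definitions in Sections 10 and 14.1, and the consequences of worsening cGVHD in 5.4/5.6 and 6.2.

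The week-16 assessment should not be moved forward for patients who stop early. For rescued patients it would change nothing, and for others it would let a response before week 16 count, which is a different endpoint.

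The cost is a few sentences and one dated field on the case report form. The observed response rate may be slightly lower. This is a scoring rule only and places no limit on rescue treatment.
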